3.0 Study Design

Cohort study of children tested with the REBIScan device followed by a vision examination.

The data will be collected using one PVS device during the child's regularly scheduled examination or on a single examination on another day at a pediatric center within the KP system. The additional examination following PVS will consist of an eye examination by a pediatric ophthalmologist. Parents and patients will be given the opportunity to complete all of the study testing during their initial visit.

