4.0 Device Information

4.1 Description of Device

The Pediatric Vision Scanner is a binocular scanner, which detects fixation in both eyes simultaneously. It detects fixation of the human eye remotely by scanning the eye with an annulus of low-intensity, polarized laser light. Previous studies have shown that it is capable of detecting strabismus in children as young as 2 years of age. Additional studies showed it could detect amblyopia in apparently straight-eyed subjects due to the high accuracy of fixation detection. REBIScan has built hand-held prototypes for clinical testing.

To allow easy operation, the PVS was equipped with a simple two-button interface and binary red-light/green light output. The device displays a binocularity score to indicate the accuracy of fixation on an internal target. A binocularity score of 60% and above (with 2 green lights) gives a "pass" recommendation; lower binocularity (with one or two red lights) results in a "refer" recommendation.

For PVS data collection, the child will be seated approximately 40 cm from the instrument fixation target. Room lights will be dimmed to enhance interest in the illuminated target and to increase pupil size. A background measurement will be obtained with eyes closed, and subtracted from subsequent readings to improve the signal to noise ratio. Data collection will last between 2.5 and 5 seconds of attention to the fixation target. Results will be recorded on the data form, but the patient, parents, and ophthalmologists will not be informed of the results.

The PVS can be operated by lay users, but some training is required, and it is possible that some individuals may have difficulty following the protocol. The Contact PI has extensive experience training users of all backgrounds in use of the device. Regular site visits by REBIScan study personnel will ensure that testing is being performed according to instruction and allow for correction of any observed problems.

In the event that meaning of the results is conveyed to a participant, caregivers, or providers, the participant will be excluded from the study and recruitment will continue until at least 300 participants who are eligible for analysis have been tested.

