5.3 Withdrawal Criteria

If a participant is unable to complete the PVS scan due to lack of cooperation, such as refusing to open one's eyes or take further direction, then the inability to participate will be recorded, and the participant will be excluded from the study, post-hoc, and not considered a part of the 300-participant cohort.

A participant may also be excluded from the study post-hoc if study personnel vocally share results of the PVS with the participant, parent, or provider prior to the Ophthalmic Examination. General observation of device indicator lights by the participant, parent, or provider is not justification for exclusion.

Finally, a participant can be excluded post-hoc if unable to complete the ophthalmic examination.

All excluded participants will be documented in the final analysis to compare how many participants were unable to perform the screening. Post-hoc exclusions at this stage will be determined by the study coordinator prior to review of the PVS screening results.

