6.0 Stratification / Descriptive Factors / Randomization Scheme

KP staff will manage all recruitment efforts for participation, as well as completing consent and data forms for all enrollees. Children who present to the pediatric clinic and meet the inclusion criteria will be invited to participate in the study until 300 participants have been enrolled and are eligible for analysis. The researcher will describe the study to their parents and obtain informed consent. The consent form will be written at a level simple enough for parents to read meaningfully and for older children to understand.

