9.0 Clinical and laboratory evaluations and study calendar

See Appendix IV, Study Workflow.

The Informed Consent, Pediatric Vision Screener (PVS) exam and Ophthalmic Exam are to be performed on the same day unless otherwise desired by the patient and/or parent/legal guardian.

	Responsibility				
	MD	MD	Tech	Tech	MD – independent
Informed Consent Discussion	X	X	X	X	
Perform Physical Examination	X	X			
Inclusion/Exclusion Criteria Review	X	X	X	X	
CRF Completion & Correction	X	X	X	X	
CRF Review & Signature	X	X			
Obtain Medical History	X	X	X	X	
Ophthalmic Exam	X	X			
PVS Exam			X		
Oversight					X

Study Calendar

Month	Task
1	Work out clinical logistics and test patient flow
2	Commence subject enrollment, 1-2 days per week
6	Submit AAPOS abstract on preliminary data
20	Complete subject enrollment
20-22	Data analysis
22-24	Report to device maker and draft JAMA manuscript

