10.0 Criteria for evaluation and endpoint definitions

The following results will be obtained when performing the PVS scan: Test length in seconds (time required to obtain a reliable scan), Yield, Tries and Binocular Score. Timing will begin once the study subject is in the chair and ready, and will conclude upon placing instrument down after all steps to acquire measurement have been completed.

At age 2-5, visual acuity testing is not always reliable or possible, and so the gold standard for this group for detection of amblyopia will be imperfect. However the goal of the study is to implement this screening tool in a pediatric practice in an effort to identify cases of strabismus and amblyopia at an early age, and therefore it is important to attempt screening at this age. Where possible, visual acuity testing will be used. In the absence of this, clinical judgement will be used to determine whether a patient has amblyopia, including fixation preference (if present), stereopsis testing, and cycloplegic refraction. It may be necessary to analyze the group in which visual acuity could be obtained separately from the group in which visual acuity could not be obtained, leaving the gold standard diagnosis uncertain. Future studies will be able to follow up on these patients later to determine whether they developed amblyopia or strabismus after referral. To standardize the way in which vision is tested all patients whose acuity is checked will be assessed using HOTV with crowding bar. Regarding logMAR testing, the problem is that the clinic is not currently set up with the acuity charts in logMAR mode, but all methods (LEA, HOTV, and Snellen) use the same standard sequence of 20/100, 20/80, 20/70, 20/50, 20/40, 20/30, 20/25, and 20/20.

The ophthalmic exam consisting of visual acuity, sensorimotor status (including stereopsis), color vision, and cycloplegic refraction will be performed by a pediatric ophthalmologist. The individual performing the ophthalmic exam will be masked to the PVS results. Stereopsis will be measured using the Preschool Random Dot Stereogram test (Stereo Optical), with the published norms to be used as the definition of reduced stereo:

Ages 2-3	≥400 arcsec
Ages 4-5	≥200 arcsec

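### Discretionary exclusion and replacement of children without a completed eye examination leave sensitivity and specificity open to partial verification bias of unknown direction

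*Protocol*

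**What the plan says.** Five provisions of the protocol bear on who reaches the accuracy analysis.

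- **Order of tests.** Section 3.0 describes a "Cohort study of children tested with the REBIScan device followed by a vision examination". The index test precedes the reference standard.
- **Visibility of the result.** Section 4.1 says that "the PVS was equipped with a simple two-button interface and binary red-light/green light output". It also says "Results will be recorded on the data form, but the patient, parents, and ophthalmologists will not be informed of the results", and it excludes a participant if the meaning of the result is conveyed. Section 5.3 excludes for results shared aloud before the examination, but adds: "General observation of device indicator lights by the participant, parent, or provider is not justification for exclusion".
- **Timing.** Under Section 9.0, consent, scan and ophthalmic examination "are to be performed on the same day unless otherwise desired by the patient and/or parent/legal guardian".
- **Exclusion and replacement.** Section 5.3 states that "a participant can be excluded post-hoc if unable to complete the ophthalmic examination". Under Section 6.0 children "will be invited to participate in the study until 300 participants have been enrolled and are eligible for analysis".
- **Reference diagnosis without acuity.** Section 10.0 makes visual acuity part of the examination but accepts that it cannot always be obtained at these ages: "In the absence of this, clinical judgement will be used to determine whether a patient has amblyopia".

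Section 5.3 has two safeguards. The study coordinator settles exclusions before reviewing PVS results, and all excluded participants are documented. Section 11.0 requires a data form for each PVS screen, with the binocularity score among the key data. Section 12.0 names sensitivity and specificity as the outputs.

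**The concern.** Sensitivity and specificity computed only in children with a completed reference examination are unbiased if completion is unrelated to the index test result, given true disease status. Here nothing secures that. A parent who has seen a light, and whose child's examination is on another day, may be more or less likely to attend. Separately, a child who cooperates poorly may both fixate badly on the scanner and fail to finish the examination, with no light being seen at all.

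The coordinator's masked decision prevents selection by the coordinator. It cannot prevent selection by families or by the child's cooperation. Replacement up to 300 keeps the sample size intact, so the loss would not show in the analysed number. The documentation of exclusions is aimed at how many children could not perform the screening. It does not ask for examination completion by PVS result, which is the table that would reveal the problem.

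The permissive wording adds to this. Section 5.3 does not define what counts as unable to complete. A young child without acuity but with a clinical-judgement diagnosis could be kept or excluded, and so could a child whose deferred examination is left unfinished.

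**Working it through.** **The plan's own figures.** Section 12.0 assumes 300 children and 5% prevalence: 300 × 0.05 = 15 cases. At the anticipated 92% sensitivity, 15 × 0.92 = 13.8 and 20 × 0.92 = 18.4, which reproduces the stated 14-18 detected out of 15-20. (Twenty cases would need 20/300 = 6.7% prevalence.) So sensitivity rests on 15-20 children, and specificity on about 300 − 15 = 285.

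**Inputs.** True sensitivity Se = 0.92 and specificity Sp = 0.82 are the anticipated values in Section 12.0. Completion after refer (v+) and after pass (v−) is not in the protocol, so every value below is an assumption.

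**Formulas.**

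Apparent Se = Se·v+ / (Se·v+ + (1 − Se)·v−)

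Apparent Sp = Sp·v− / (Sp·v− + (1 − Sp)·v+)

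**Worked case, v+ = 0.95 and v− = 0.80 in the whole cohort.**

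Se: 0.874 / (0.874 + 0.064) = 93.2%

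Sp: 0.656 / (0.656 + 0.171) = 79.3%

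**Range when the rates apply to the whole cohort.**

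| v+ / v− | Apparent Se | Apparent Sp |
|---|---|---|
| 80% / 80% | 92.0% | 82.0% |
| 95% / 90% | 92.4% | 81.2% |
| 95% / 80% | 93.2% | 79.3% |
| 90% / 60% | 94.5% | 75.2% |
| 60% / 95% | 87.9% | 87.8% |

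Equal completion gives no bias. The last row shows that the direction reverses when completion is lower after refer.

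**Range when only a fraction d defer.** Same-day testing is the default, so suppose all other children complete and the rates r+ and r− apply to deferring children only: v+ = (1 − d) + d·r+, and likewise for v−.

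| d | r+ / r− | v+ / v− | Apparent Se | Apparent Sp |
|---|---|---|---|---|
| 10% | 95% / 80% | 0.995 / 0.98 | 92.1% | 81.8% |
| 30% | 95% / 80% | 0.985 / 0.94 | 92.3% | 81.3% |
| 10% | 90% / 60% | 0.99 / 0.96 | 92.2% | 81.5% |
| 30% | 90% / 60% | 0.97 / 0.88 | 92.7% | 80.5% |

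At 95%/80% the shift is at most 0.7 points. At 90%/60% it reaches 1.5 points.

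**Scale against sampling error.** For specificity, 1.96 × √(0.82 × 0.18 / 285) = 4.5 points. For sensitivity, the exact 95% interval for 14/15 is 68.1% to 99.8%.

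**Sensitivity to single children.** With so few cases, a handful of losses can matter. If 12 of 15 cases are detected (80.0%) and two of the three missed cases go unverified, the estimate becomes 12/13 = 92.3%.

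**The case against.** The case against is substantial, and most of it limits the size of the point.

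- **Deferral in response to the lights.** A reader might infer that families see the result and then put off the examination. No passage says so. Section 9.0 covers consent, scan and examination together, and Section 3.0 speaks of a single examination on another day and offers all testing at the initial visit. The testing may well move as a block, before any light is seen. A split visit is permitted, but the causal link is only possible.
- **Inability versus non-return.** The quoted rule is about being unable to complete, and it permits exclusion without requiring it. It does not clearly cover a family that does not come back. Still, a child with no reference diagnosis cannot enter either denominator, whatever the label.
- **Sections 5.3 and 10.0.** It is tempting to call these contradictory. They are not: Section 10.0 gives a child without acuity a diagnosis by clinical judgement and foresees separate analysis, and the word 'can' in Section 5.3 is compatible with that. What remains is an undefined term.
- **Existing safeguards.** Section 4.1 excludes where the meaning of a result is conveyed, and Section 11.0 already records a PVS form for each screen. Both stand. Neither yields completion by PVS result.
- **Analysis detail.** A verification correction could sit in an SAP that is not shown, so its absence is not the finding. The exclusion and replacement rule is fixed in the protocol, and that is the finding.

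**Conclusion.** The point holds as a weakness in the exclusion rule, not as a demonstrated bias. The protocol allows discretionary exclusion after the index test, replaces the excluded children, tolerates visible results and lets the examination fall on another day. Completion could therefore depend on the PVS result or on a correlate of it.

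The size is unknown because the protocol gives no completion rates. Shifts of about 3 to 7 points in specificity need 20-40% of all PVS-negative children to go unverified, which is hard to square with same-day testing as the default. With 10-30% deferring at 95%/80% completion the shift is under 1 point, well inside the sampling error of about ±4.5 points.

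Two stronger conclusions are not supported. The direction is not fixed, so one cannot say that sensitivity will be too high and specificity too low. Nor should the shift be judged against a 5-point margin: the 5% in Section 12.0 describes anticipated agreement with published values and is not an acceptance limit.

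The hypothesis in Section 2.2 concerns children who screen positive. It is unaffected if completion depends only on the PVS result. The Section 12.0 outputs are the ones exposed.

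**What to change.** 1. In Section 5.3, limit this exclusion to children for whom no reference diagnosis can be made, whether acuity-based or by clinical judgement under Section 10.0. State it as a rule in place of the permissive 'can be'.
2. For every child with a completed scan, tabulate examination completion by PVS result (refer or pass), including the children who were replaced.
3. If completion differs by result, report beside the complete-case sensitivity and specificity either a Begg-Greenes estimate, which weights verified children by 1/v+ or 1/v−, or best/worst-case bounds. Do not stratify the correction by age: 15-20 cases are too few.

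The cost is a wording change and a little analysis on results that Section 11.0 already collects. The correction assumes that completion depends only on the PVS result. It would not fully remove bias that arises through cooperation, because uncooperative children who are referred may differ in disease status from other referred children. The bounds need no such assumption, but they will be wide if the unverified children are many relative to the 15-20 cases.

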6.0 Stratification / Descriptive Factors / Randomization Scheme

KP staff will manage all recruitment efforts for participation, as well as completing consent and data forms for all enrollees. Children who present to the pediatric clinic and meet the inclusion criteria will be invited to participate in the study until 300 participants have been enrolled and are eligible for analysis. The researcher will describe the study to their parents and obtain informed consent. The consent form will be written at a level simple enough for parents to read meaningfully and for older children to understand.

7.0 Study Agent administration or intervention and toxicity management plan

Not applicable

8.0 Assessment of efficacy and safety

The primary efficacy outcome is amblyopia, defined as a two or more line difference between the eyes or a clear fixation preference in either eye:

- 2-3 year old: vision >20/50
- 4 year old - vision > 20/40
- 5 year old - vision > 20/30

; and/or the presence of strabismus, defined as the misalignment of the eyes.

The device is considered a non-significant risk device. As such, no risk is expected with its use.

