NCT Number: NCT02536963

Study Title: Improving Quality Vision Outcomes in Managed Care Setting While Reducing Cost by Use of Accurate, Automated Screening

Document: Study Protocol

Date Created: August 2015

Objectives and Purpose

2.1 The purpose of this study is to assess the performance of the Pediatric Vision Scanner at identifying amblyopia/strabismus on children older or equal to 2 years of age, and less than 6 years of age in a busy pediatric clinic setting and to compare it to an examination comprised of visual acuity testing, stereopsis, eye alignment, and cycloplegic refraction.

2.2 The hypothesis is that the false positive rate of REBIScan is 10% or less. The proportion of patients without amblyopia or strabismus will be less than 10% of patients screened positive by the device.

- Amblyopia will be defined as a two or more line difference between the eyes or a clear fixation preference in either eye, in the presence of a known amblyogenic factor.
 - 2-3 year old: vision >20/50
 - 4 year old - vision > 20/40
 - 5 year old - vision > 20/30
- Strabismus is defined as misalignment of the eyes.

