12.0 Statistical considerations

This study is the second of a two-phased study. The first phase was a pilot and feasibility study to understand the utility of using the PVS device within Kaiser Permanente. This second phase is to determine the sensitivity and specificity of the device and its feasibility for widespread deployment in a primary care setting.

The collected data will generate patient demographic and clinical descriptives to describe the study population.

The outputs that will be calculated are sensitivity and specificity for detecting amblyopia or strabismus. The current published data on PVS sensitivity and specificity is 97% and 87% respectively. Error! Bookmark not defined. It is anticipated that sensitivity will be within 5% of the published results; that is, 92% sensitivity and 82% specificity (contained within the calculated 95% confidence intervals.) Assuming a 5% prevalence rate of the conditions, in a sample size of 300 children we anticipate 15-20 children presenting with amblyopia or strabismus; therefore we expect to identify 14-18 cases, while having no more than 45 false referrals.

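### Section 8.0 names the reference diagnosis as the primary outcome, under a case definition that differs from 2.2, and the 10% hypothesis is ambiguous and at odds with Section 12's own figures

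*Protocol*

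**What the plan says.** Four places in the protocol bear on what the study is meant to show.

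- **2.1 (purpose):** "The purpose of this study is to assess the performance of the Pediatric Vision Scanner at identifying amblyopia/strabismus", judged against an eye examination.
- **2.2 (hypothesis):** two consecutive sentences. The first: "The hypothesis is that the false positive rate of REBIScan is 10% or less". The second: "The proportion of patients without amblyopia or strabismus will be less than 10% of patients screened positive by the device". The case definition that follows counts amblyopia only if a known amblyogenic factor is also present.
- **8.0 (efficacy):** "The primary efficacy outcome is amblyopia, defined as a two or more line difference between the eyes", or a fixation preference, with age-specific acuity limits, and/or strabismus. The amblyogenic-factor condition does not appear.
- **12.0 (statistics):** "This second phase is to determine the sensitivity and specificity of the device and its feasibility for widespread deployment in a primary care setting". "The outputs that will be calculated are sensitivity and specificity for detecting amblyopia or strabismus". The benchmark is the literature: "The current published data on PVS sensitivity and specificity is 97% and 87% respectively". The anticipated result is "92% sensitivity and 82% specificity (contained within the calculated 95% confidence intervals". With 5% prevalence and 300 children, Section 12 expects 15–20 affected children, 14–18 of them identified, and at most 45 false referrals. The 10% of 2.2 is not mentioned.

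**The concern.** A primary outcome for an accuracy study has to combine the index test with the reference standard. Section 8.0 uses the reference standard alone, so its primary outcome would take the same value however well or badly the scanner worked.

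The hypothesis does not repair this. Its two sentences use different denominators: unaffected children in the usual meaning of false positive rate, and device-positive children in the second sentence. Section 12 then works with sensitivity and specificity against published values and leaves the 10% aside.

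Two things are at stake. With no accuracy measure fixed as primary, specificity, sensitivity or PPV could each be presented as the main result once the data are known. And with two case definitions, some children can change cells in the 2×2 table depending on which section the analyst follows.

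**Working it through.** **Inputs (Section 12 unless noted).** N = 300; prevalence 5%; 15–20 cases; published sensitivity/specificity 97%/87%; anticipated 92%/82%; 14–18 true and at most 45 false referrals; threshold 10% (2.2).

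**1. Reproducing the plan's counts.**
- Cases: 300 × 0.05 = 15. The upper figure of 20 corresponds to 20/300 = 6.7%.
- True referrals: 15 × 0.92 = 13.8 and 20 × 0.92 = 18.4, so 14–18 reproduces.
- False referrals with 285 unaffected: 285 × 0.18 = 51.3 at 82% specificity; 285 × 0.13 = 37.1 at 87%. The stated 45 equals 300 × 0.15, and 15% is a rate the protocol does not state. As a ceiling, 45 holds at 87% but not at 82%.

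**2. The Section 8.0 outcome taken literally.** 15/300 = 5%, exact 95% CI 2.8–8.1%. This is a prevalence.

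**3. First sentence of 2.2, read as 1 − specificity ≤ 10%.** This needs at most 28 false positives among 285 (28/285 = 9.8%; 29/285 = 10.2%).

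| Source in Section 12 | False positives of 285 | Rate | Exact 95% CI |
|---|---|---|---|
| Specificity 87% | 37 | 13% | 9.3–17.5% |
| Ceiling of 45 | 45 | 15.8% | 11.8–20.6% |
| Specificity 82% | 51 | 18% | 13.6–22.9% |

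If the true rate is 13%, the binomial probability of observing 28 or fewer of 285 is 6.2%. If it is 18%, the probability is below 0.01%. No significance level is needed for this comparison.

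**4. Second sentence of 2.2, 1 − PPV = FP/(TP + FP) < 10%.**
- From the stated counts: 45/(45 + 14) = 76.3%; 45/(45 + 18) = 71.4%.
- From the accuracy figures at 15 and 20 cases: with 92%/82%, 51.3/65.1 = 78.8% and 50.4/68.8 = 73.3%; with 97%/87%, 37.05/51.6 = 71.8% and 36.4/55.8 = 65.2%.
- To be under 10%, FP must be below TP/9: 14/9 = 1.6 or 18/9 = 2.0. So fewer than about two false referrals are allowed, which needs specificity of about 99.3–99.5%.
- The two sentences are far apart. Meeting the first at its limit (28 false positives) still gives 28/(28 + 14) = 66.7% or 28/(28 + 18) = 60.9% on the second.

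**5. The two case definitions.** A child who meets the acuity or fixation criterion without a known amblyogenic factor, and who has no strabismus, is a case under 8.0 and a non-case under 2.2. If the PVS refers the child, the result is a true positive under 8.0 and a false positive under 2.2. If the PVS passes the child, it is a false negative under 8.0 and a true negative under 2.2. The protocol does not say how many such children to expect. As an illustration, one passed child of this kind takes sensitivity from 14/15 = 93.3% to 14/16 = 87.5%.

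**The case against.** The strongest reply is that Section 8.0 only defines the target condition under a template heading. Read with 2.1 and Section 12, no analyst would report disease frequency as the result. That is likely true of practice, and the 5% figure shows what the words say, not what the sponsor would do. But no other section names a primary outcome, so the misstatement stands.

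A reader might also infer that the hypothesis is never tested. The protocol does not support that. In the usual sense the false positive rate is 1 − specificity, and Section 12 plans specificity and refers to 95% confidence intervals, so the first sentence of 2.2 will be estimated. PPV could be computed from the same 2×2 table, and a formal comparison may sit in a statistical analysis plan that is not shown. What remains is narrower: the protocol does not connect its outputs to the 10%, does not settle which quantity the 10% concerns, and gives figures that conflict with it. An analysis plan would have to choose between conflicting protocol statements.

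It is equally tempting to read 2.2 as already meaning 1 − specificity. The second sentence prevents this, because its denominator is the children who screen positive.

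Finally, 45 is a ceiling, and being within 5 points of 87% could be read upward as 92% specificity, a false positive rate of 8%, which meets the first sentence. Section 12 names only the lower values. Even at 92% specificity and 97% sensitivity, 1 − PPV is 22.8/37.35 = 61% with 15 cases and 22.4/41.8 = 54% with 20, so the second sentence still fails.

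**Conclusion.** The point holds in a limited form. Section 8.0 names the condition and not a measure of the device, and its definition of amblyopia is wider than that in 2.2. These are stated errors and not details left for later. The 10% hypothesis carries two meanings, and the plan's own expectations miss it under both: 13–18% for 1 − specificity and 71–76% for 1 − PPV at the stated referral counts.

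These sizes rest on Section 12's 5% prevalence and 300 analysable children (285 unaffected), with the PPV range covering its 14–18 true referrals. At 87% specificity the 95% interval for the false positive rate would still include 10%, so on the first sentence the conflict lies in the expected value and in the low chance of observing 10% or less. It is not a certainty of refutation. No confidence level or sidedness for a test is assumed, since the protocol states none. Nor do the documents rank sensitivity against specificity.

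**What to change.** - **2.2:** state whether the 10% refers to unaffected children who screen positive (1 − specificity) or to screen-positive children who are unaffected (1 − PPV), with the denominator written out. Drop or relabel the other sentence.
- **8.0:** name that accuracy measure, PVS pass/refer against the reference diagnosis, as the primary outcome. Keep amblyopia and/or strabismus as the reference standard.
- **2.2 and 8.0:** use one identical case definition. The sponsor should decide whether the amblyogenic-factor condition belongs in it.
- **12.0:** say how the confidence interval of the chosen measure is compared with the threshold, report sensitivity and specificity with exact intervals, and reconcile the 10% with the anticipated 82–87% specificity and the 45 false referrals.

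The cost is wording in three sections, with no new data or visits. The downside is that it becomes visible that the 10% hypothesis is unlikely to be met at the specificity the plan itself anticipates, so the sponsor may have to revise the threshold or justify it.
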